### Primary Outcome – Metabolic Syndrome Biomarkers

Anthropometric measurements (body mass index, waist circumference and percentage of body fat) and blood pressure are taken during each follow-up sessions based on the WHO Protocol (27). Blood clinical outcomes will be screened using rapid finger-prick testing method; glucometer (B Braun Omnitest®3, Germany) and blood lipid profile meter (Cardiocheck® PA, Germany), as it is an accurate and sensitive method to cater a community setting intervention (28). Besides, a bio-impedance body composition analyser (InBody® H2OB Analyser, Korea) will be used to estimate fat and muscle percentage of the participants.

### Secondary Outcome – Dietary Pattern, Physical Activity Levels and Lifestyle Behaviour

A three days 24-hour dietary recall is used to analyse the nutrient intake. The recall will be done in a week timeframe with three non-consecutive days will be randomly selected (29). Physical Activity levels are measured using the validated short-form International Physical Activity Questionnaire (IPAQ) (30) while a short questionnaire on sleeping pattern, smoking and alcohol intake is used to elucidate lifestyle behaviour.

### Process Evaluation

A questionnaire will be developed and validated to measure the self-efficacy change of all peers at two levels; individual and peer group. Adherence to the intervention is assessed by the number of posters collected by all participants at the end of the peer support period. Other than that, PL is responsible to record all peer attendance throughout the three months period. Eventually, the participants' satisfaction of the intervention will be assessed by self-administered questionnaire at post-intervention.

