### Peer Leader Selection

As an elaboration to the study flowchart (Figure 2), the intervention group will form a minimum number of eight peer groups with two PL will be selected from each group on voluntarily basis. PL will be trained for the all four modules and an extra module; health promotion. This module aimed at assessing appointed PL for leadership, health educator role, and understanding of the PERSUADE modules. All PL attended a two-days training session on focussing on leadership and communication skills. On top of that, a practical approach will be used, including physical, nutritional, and psychological aspects of a lifestyle change as included in all four PERSUADE modules. PL will be trained to engage with their peers in conversations about the issues of concern, seeking to promote health-enhancing knowledge and skills. The goal for each peer group is to be able to identify potential barriers and determinants of lifestyle improvement and subsequently take actions to reduce their CVD risk. At the end of PL training, a simple post-questionnaire will be distributed among them to indicate validity and adequateness of their knowledge and skills on all peer modules.

Respective PL will distribute the posters among their peer group every week to initiate discussion of relevant topics based on the weekly objectives. In order to maximise the participation, regular reminder about the next peer gathering sessions and short health message through text were regularly sent by PL. Peers will then have to keep the poster and returned it to the PL at the end of three months as a measure of compliance to the peer support program. Besides, peers are also encouraged to distribute the poster as a health promotion steps among the community.

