### Process Evaluation

Furthermore, PERSUADE combines the HBM concept in a peer support framework. The use of theoretical construct in this study allows the outcome evaluation to be supplemented by an adjunct process evaluation. The process evaluation will measure the degree of knowledge delivered and received, fidelity of acquired skills and its implementation as well as the participants' acceptability and satisfaction with the program. Similar to all peer-based interventions, this trial's reach is highly dependent on the participants' compliance based on the peer attendance rates and usability of PERSUADE materials. Collectively, these measures will enable us to resolve any enhancers and barriers of a peer-based program if the program were to be harnessed in other settings and context.

As a conclusion, PERSUADE is a three months community peer support nutrition and lifestyle behaviour peer support intervention for Malaysian adults with MetS. Peer support is a cost-effective, straightforward and sustainable measure to combat lifestyle-related diseases. Thus, a feasibility study among Malaysian adults is designed as RCT to elucidate its acceptance and effectiveness. As PERSUADE modules were theoretical, evidence-based and community-specific, the overall improvement in metabolic risk profile is greatly expected prior to nutrition and lifestyle behaviour improvement.

Table and Figures

Figure 1: Conceptual framework of PERSUADE peer support program

[figure not shown]

Figure 2: PERSUADE peer support program randomised controlled trial flow chart

[figure not shown]

Table 1: PERSUADE inclusion and exclusion criteria

Inclusion Criteria	Exclusion Criteria
Physically healthy men and women who are $\geq 18$ years old.	Pregnant, lactating or intend to become pregnant during the study period.
Literate with a fair command of Bahasa Melayu and/or English.	Diagnosed with Type 1 Diabetes Mellitus (T1DM)
Have been confirmed of having MetS according to Harmonised Criteria (46, 47).	Any predisposing condition compromising the quality of life or ability to participate according to protocol.
Willing to attend weekly peer gathering sessions.	Reported severe complications (chronic heart disease, cerebrovascular disease, diagnosed HIV/AIDS, cancer, emphysema, chronic liver or kidney disease) that would affect the participants' ability to follow the participation in peer activity.

Table 2: PERSUADE behavioural change matrix

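### Adherence is scored by posters returned while participants are encouraged to give posters away, so the count reads low for those who do so unless extra copies are supplied (minor)

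*Combined protocol and SAP*

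**What the plan says.** Two sections of the combined protocol and SAP bear on this.

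- **Outcome Assessment, Process Evaluation** names the measure: "Adherence to the intervention is assessed by the number of posters collected by all participants at the end of the peer support period". It adds a second record of exposure, "PL is responsible to record all peer attendance throughout the three months period", and a separate measure of acceptance, under which "satisfaction of the intervention will be assessed by self-administered questionnaire at post-intervention".
- **Peer Leader Selection** says how the poster number arises. "Respective PL will distribute the posters among their peer group every week", and at the end of the programme "Peers will then have to keep the poster and returned it to the PL at the end of three months as a measure of compliance". The very next sentence says that "peers are also encouraged to distribute the poster as a health promotion steps among the community".

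The Process Evaluation part of the Discussion sets out what these data are for. It rests compliance on attendance rates and on how usable the materials prove to be, expects that "these measures will enable us to resolve any enhancers and barriers of a peer-based program", and concludes that "a feasibility study among Malaysian adults is designed as RCT to elucidate its acceptance and effectiveness".

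The available text mentions no spare copies, no log of posters handed out, and no rule for scoring a poster that has been passed on.

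**The concern.** The same poster is asked to do two jobs. It is the token of compliance, to be held and handed back, and it is also promotional material, to be passed to others. A poster given to a neighbour cannot be returned. Read literally, the score falls for a participant who does what the programme encourages, and it cannot tell that person from someone who never received the poster or lost it.

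What is at stake is the interpretation of one process measure. Feasibility is a stated purpose in the Study Design section, and adherence is part of any feasibility account. A low return rate could be read as poor uptake when it partly reflects posters put to their intended second use.

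**Working it through.** The plan gives no adherence figure to reproduce. The check is a reading of the text, followed by illustrations whose inputs are marked as planned or assumed.

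**1. Which count is meant.** Posters collected by participants could mean posters received. On that reading there would be no bias, since giving a poster away does not undo having received it. Peer Leader Selection, however, ties compliance explicitly to posters kept and returned, so returned posters is the natural reading.

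**2. Direction of the bias.** For one participant let A be posters received, k the share kept to the end or deliberately passed on (that is, not lost or discarded), and g the share of those passed on. Posters returned = A × k × (1 − g). For any g above 0 the return falls below A × k. With no separate copies, giving posters away can only lower the score.

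**3. Size, by assumption.** No value of g is stated. Taking k = 80% (assumed):

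| Share passed on, g (assumed) | Score = 80% × (1 − g) |
|---|---|
| 0% | 80% |
| 10% | 72% |
| 25% | 60% |
| 50% | 40% |

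**4. Two participants compared.** Table 2 lists 1 + 4 + 4 + 3 = 12 infographics over its four themes. That fits weekly hand-outs over three months, although the plan does not state a number of posters per person. Someone who attends all 12 sessions and gives away 4 posters returns (12 − 4)/12 = 67%. Someone who attends 8 and gives away none returns 8/12 = 67%. The count cannot separate them. Beyond a give-away share of 1 − 8/12 = 33%, the full attender scores lower.

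**5. Does the count still track attendance?** Assume 48 people (the planned arm size), sessions attended uniform on 6 to 12 (mean 9, variance 4), one poster per session, and each poster passed on with probability g. If g is the same for everyone, the correlation of posters returned with sessions attended is √[4(1 − g) / (4(1 − g) + 9g)].

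- g = 30%: √(2.8 / 5.5) = 0.71
- g = 50%: √(2.0 / 6.5) = 0.55

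If the share passed on instead rises in a straight line from 0 at 6 sessions to g at 12 sessions, simulation (4,000 repeats) gives about 0.59 at g = 30%, 0.00 at 50% and −0.28 at 60%. Simulation of the constant-share case agrees with the formula.

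The count loses information under either assumption. It stops tracking attendance, or reverses, only if better attenders give away a larger share. Nothing in the documents says whether they do.

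**6. What the bias reaches.** Attendance is logged separately and does not depend on what happens to a poster. Satisfaction has its own questionnaire. The Statistical Analysis section plans no analysis that uses poster counts: no per-protocol set, no adherence threshold, no dose-response model. The repeated-measures comparison of the clinical outcomes is untouched.

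**The case against.** The strongest reply is that adherence does not rest on posters alone. Attendance is recorded throughout the three months, and the Discussion names attendance as a basis for compliance, so a sound indicator sits beside the flawed one. This stands, and it is the main reason the point is minor. It does not remove the point, because the section that defines adherence assigns it to posters and the plan does not say which measure prevails if the two disagree.

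A second reply is that distributing a poster may mean showing it round or handing out extra copies, in which case keeping and returning it is compatible with sharing. That is possible. The text does not settle it, and for this reason the conclusion is conditional on there being no extra copies.

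Three stronger readings are tempting, and the documents do not support them.

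- *A reader might infer that the acceptance and barriers results would be distorted by the poster rule.* The poster count feeds neither the satisfaction questionnaire nor any planned analysis.
- *A reader might infer that the score ranks engaged people below less engaged ones.* This can happen for particular pairs, as in step 4. A reversal across the whole group needs the added assumption in step 5 that giving away rises with attendance.
- *A reader might infer that the plan fails to capture why people stop, so that acceptance reflects only those who stay.* The available text describes no recording of reasons, and the sample size section allows for 20% dropout (0.20 × 48 = 9.6 people per arm). But the flow chart (Figure 2) is not shown, the questionnaires are not reproduced, the Study Design section follows CONSORT, and the satisfaction measure is not restricted to completers. This is an argument from silence and not a demonstrated error.

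**Conclusion.** The point holds in a limited form. As written, and unless separate copies are supplied, the returned-poster count is biased downwards as a measure of adherence, because it marks down participants who distribute posters as encouraged. The direction follows from the text. The size cannot be computed, since neither a give-away rate nor a number of posters per participant is stated, and the figures above are illustrations under assumed values.

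Severity is minor: one process indicator is affected, and a better one is already being collected. The sample size and the effectiveness conclusion do not depend on it.

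**What to change.** 1. Define adherence as sessions attended, taken from the attendance log that peer leaders already keep. This agrees with the Discussion and needs no new data.
2. If posters are kept as a secondary measure, add a tick column to that log and mark each poster when it is handed out, instead of counting returns. Alternatively, supply separate copies for distribution so that the participant's own set can still be returned.
3. State which measure is the main one if the two disagree.

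The cost is one column on an existing form, or some extra printing. The downside is that, if returns are dropped, they no longer act as a physical check on a log kept by peer leaders. Research staff can replace that check by comparing the log with an occasional headcount, for example at one or two sessions per group.

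A sensible minor addition is to note the date and main reason when anyone stops, using the same short list in both arms, and to report satisfaction over all participants assigned to the intervention with the number not answering. If the 20% allowance were reached, this would mean a short call to about 10 people per arm. The primary analysis does not change.

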## Study Sample

### Sample Size and Power Calculation

The estimated sample size based on earlier similar study (10) on one the study variables, fasting plasma glucose at 95% confidence and 80% power of an anticipated fall in FPG of 1.5 to 1.8 mmol/L. Using an equation to detect changes in a standard parallel-group trial and a 20% drop out rate, the calculated minimum required sample size is 48 participants for each group thus the totalling 96 for both randomized arm.

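### Satisfaction is measured once, at the end and at peer gatherings, and no reason for stopping is recorded, so acceptability and barrier findings would come mainly from peers still attending

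*Combined protocol and SAP*

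**What the plan says.** Four process measures are described in the Process Evaluation section under Outcome Assessment:

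- **Satisfaction:** a single measurement, "satisfaction of the intervention will be assessed by self-administered questionnaire at post-intervention".
- **Attendance:** "PL is responsible to record all peer attendance throughout the three months period".
- **Adherence:** "Adherence to the intervention is assessed by the number of posters collected by all participants at the end of the peer support period". Peer Leader Selection gives the mechanism: "Peers will then have to keep the poster and returned it to the PL at the end of three months".
- **Self-efficacy:** a questionnaire, still to be developed, to "measure the self-efficacy change of all peers at two levels", with no time points stated.

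The opening text of Outcome Assessment places all assessments at peer gatherings, carried out by the research team with help from peer leaders.

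The Discussion draws conclusions from these measures. Its Process Evaluation section says: "Collectively, these measures will enable us to resolve any enhancers and barriers of a peer-based program". The same section describes the purpose of the trial: "a feasibility study among Malaysian adults is designed as RCT to elucidate its acceptance and effectiveness". The sample size section allows for a "20% drop out rate".

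**The concern.** Acceptance is a stated purpose of the trial, and the plan expects some participants to be lost. Yet the one acceptability measure comes at the end of the three months, in a setting that peers who stopped have left. Nothing visible asks them for a reason, either when they stop or later.

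Two conclusions are exposed. A satisfaction figure drawn mainly from those still attending is likely to be higher than the figure for everyone offered the programme. A list of barriers drawn from the same people would cover obstacles that could be tolerated and largely miss those strong enough to end participation. The Discussion presents barriers as something that others could use when taking the programme to new settings, so that omission matters.

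**Working it through.** **Step 1. What each measure can show about a peer who stops in, say, week 3.**

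| Measure | What it shows | What it does not show |
|---|---|---|
| Attendance record (weekly gatherings, kept throughout) | That the peer stopped, and the last week attended | Why |
| Poster count (end of three months) | Low adherence, if the posters are returned or counted as absent | Why |
| Self-efficacy questionnaire (time points not stated) | Possibly a change score, if the peer is reached | Why; acceptability |
| Satisfaction form (post-intervention, self-administered) | Acceptability, if the peer is reached | No route to a peer who has left is described |

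Table 3 lists no exit form and no field for a reason for stopping. The Statistical Analysis section gives no denominator for satisfaction. The focus groups were held while the modules were being developed, so they cannot reveal barriers met during this programme.

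**Step 2. Size of the effect on the satisfaction figure.** The plan states no satisfaction figure, so there is none to reproduce.

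Inputs from the documents:
- 48 participants in the intervention group (Sample Size and Power Calculation), taken as given.
- Drop-out allowance of 20% (same section).

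Assumptions, not in the documents:
- The 20% applies to non-return of this form; call it d.
- Satisfaction can be summarised as satisfied or not.
- 90% of responders are satisfied; call this p_R. The rate among non-responders is p_N.

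Number not responding: 0.20 × 48 = 9.6, or about 10, leaving about 38.

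Value among all allocated = (1 − d) × p_R + d × p_N. Overstatement = p_R − that value = d × (p_R − p_N).

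| p_N | All allocated | Responders-only figure minus all allocated |
|---|---|---|
| 0% (worst case) | 0.8 × 0.90 + 0.2 × 0 = 72% | +18 points |
| 30% | 0.8 × 0.90 + 0.2 × 0.30 = 78% | +12 points |
| 60% | 0.8 × 0.90 + 0.2 × 0.60 = 84% | +6 points |
| 90% | 0.8 × 0.90 + 0.2 × 0.90 = 90% | 0 points |
| 100% (best case) | 0.8 × 0.90 + 0.2 × 1 = 92% | −2 points |

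**Step 3. Sensitivity to the two assumed inputs.** The bounds are (1 − d) × p_R and (1 − d) × p_R + d. With p_R = 80%:

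| d | Bounds for all allocated |
|---|---|
| 10% | 72% to 82% |
| 20% | 64% to 84% |
| 30% | 56% to 86% |
| 40% | 48% to 88% |

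The width of the range equals the non-response share. The range is lopsided: when most responders are satisfied, there is far more room below the reported figure than above it.

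**The case against.** Much can be said for the plan.

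- **Attendance is recorded throughout for all peers.** A reader might infer that the timing of stopping is lost, or that the feasibility findings as a whole would be flattered. The documents do not support either. Gatherings are weekly, so the last week attended can be read from the record, and early stopping lowers attendance. Only the reason for stopping and the leavers' views are missing.
- **The satisfaction form is not restricted to completers.** This is correct. That leavers would mostly not return it is an inference from where assessments take place and from the lack of any described way to reach leavers. It is not a stated rule. Likewise, an all-allocated denominator fills a silence and does not correct an error.
- **The 20% is a drop-out allowance for the sample size in both arms.** It does not forecast how many intervention peers will stop attending and leave the form unanswered. Someone may stop attending and still be assessed at month 3. The percentages above are therefore illustrations.
- **The process evaluation is adjunct.** The primary aim concerns the metabolic syndrome components, and that comparison does not depend on the satisfaction form. A reader might also see satisfaction as driving the policy remark in the Discussion, but that remark is conditional on success in general and does not mention satisfaction.
- **Figure 2 is not shown.** What it says about withdrawals cannot be checked.

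These points narrow the concern but do not remove it: none supplies a reason for stopping or a way of obtaining leavers' views.

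**Conclusion.** The concern holds in a limited form. Followed as written, the plan would obtain acceptability and barrier data mainly from peers still attending, with no reason recorded for those who stop. That falls short of the barrier claim in the Discussion.

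It is tempting to say that reported satisfaction will certainly be too high. The documents support only that this is likely: it requires leavers to be both less satisfied and less likely to respond. If they were as satisfied as the rest, there would be no overstatement, and in the best case the figure would be 2 points too low. Under the assumed 20% non-response and 90% satisfaction among responders, the overstatement is 6 to 12 points if 60% down to 30% of non-responders would be satisfied. None of these satisfaction rates comes from the documents.

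**What to change.** Amend the Process Evaluation section under Outcome Assessment as follows.

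1. Add a field for the main reason for stopping. The research team, not the peer leader, completes it when a peer says they are stopping, or otherwise at the month-3 contact. Peer leaders deliver the programme, so a peer may be less frank with them.
2. Give the existing satisfaction form at month 3 to every participant allocated to the intervention, by post or phone if they no longer attend.
3. Report satisfaction with all participants allocated to the intervention as the denominator, broken down by attendance level, with best-case and worst-case bounds for non-responders.

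A call triggered by missed gatherings while the programme is running is better avoided: it could prompt people to return and so alter the attendance being measured. The price of waiting is that some reasons will be recalled at month 3.

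The cost is a small number of extra contacts, about 10 of 48 if 20% stop, and a satisfaction figure that may be less favourable. The sample size, the intervention and the primary analysis do not change.

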### Other Measurements

The socio-demographic characteristics of all participants will be recorded in a structured questionnaire at baselines. Participants' quality of life will also be recorded using a validated questionnaire (31, 32).

